
Primary study endpoint
	
This is set on visit 3 (90 ± 5 days from the date of visit 1). The two groups of vaccination are compared for the primary endpoints which is composite. Patients who meet any of the following will be considered to meet the primary endpoint:
 
 • Positive for the respiratory questionnaire endpoint when at least one of the following combination is met either at visit 2 and/or at visit 3: 
 ➢ One situation definitively related to COVID-19 ➢ All four questions of symptoms possibly related to COVID-19 answered YES ➢ At least two questions of symptoms possibly related to COVID-19 answered YES + need for admission at the emergency department of any hospital and/or need for intake of antibiotics answered YES ➢ At least four questions of symptoms probably related to COVID-19 answered YES one of which is “need for admission at the emergency department of any hospital and/or need for intake of antibiotics” • Positive IgG or IgM antibodies against SARS-CoV-2

Secondary study endpoints
	
 • Positive respiratory questionnaire endpoint (as defined above) on visit 4 • Positive respiratory questionnaire endpoint (as defined above) on visit 5 • Prevalence of IgG/IgM against SARS-CoV-2 among the total of screened participants • Itemized analysis of each of the components of the respiratory questionnaire on each study visit • The impact of new cardiovascular events on each study visit • The differences in repeated measurements of vascular parameters

	
(arterial hardness, central arterial pressures, reflected waves, endothelial function and thickness of medial carotid sheath) in the visit 3 between the two groups (placebo or BCG)
 
 • The differences in repeated measurements of vascular parameters (arterial hardness, central arterial pressures, reflected waves, endothelial function and thickness of the medial carotid sheath) and cardiac echocardiogram on the ECG visit (visit BCG) between the two sub-study groups • Changes in the release of cytokines from blood mononuclear cells at visit 3 between the two sub-study groups (placebo or BCG)
Power of the study	
The study is powered for the primary endpoint. The results of the interim analysis of the ACTIVATE study reveal 20.4% incidence of total respiratory infections after three months from vaccination in the placebo group and 12.2% in the BCG group. To demonstrate this difference with 90% power at the 5% level of significance, 437 people need to be vaccinated per group. To adjust for losses to follow-up, we target to enroll 450 people per group.
 
To estimate the power of the sub-study, it is anticipated that there will be a difference greater or equal to 2% in endothelial-dependent vasodilation between the two interventions in visit 5. It is estimated that a total sample of 68 patients (equally 34 individuals in each study group-placebo and BCG) will highlight the difference with 80% power at a statistical significance level of 10%. In order to adjust for possible loss of 10%, it is estimated that 75 patients should be admitted to the sub-study.

Interim analysis	
Taking into consideration the situation of COVID-19 pandemic, an interim analysis is decided by the Sponsor when all patients reach visit 3

Study duration	
12 months

BACKGROUND

Infection by the novel SARS-CoV-2 virus (also known as COVID-19) has tremendous social impact. Most of Western societies are at major or part lockdown whatever brings unpredictable financial and societal consequences. The urgent need for the reversal of this situation can only be met through the generation of an immune defence shield to protect the society from COVID-19. Many efforts for the development of a vaccine are under way without any specific outcome so far.

The stimulation of trained immune responses seems the only alternative to bridge the gap from the turn-on of the society until the entrance of a specific vaccine in the market. Trained immunity stands for the non-specific raise of defence shield for severe infections coming once tissue macrophages recognize a universal pathogen¹. The concept was successfully tested in healthy volunteers that were vaccinated with placebo or BCG (Bacillus Calmette Guérin) vaccine. These volunteers were injected 14 days later a tri-valent influenza A vaccine. Volunteers previously vaccinated by BCG developed significantly greater titres against hemagglutinin A of the influenza A virus whereas their circulating monocytes were more potent for the production of interferon-gamma².

It is proposed that this BCG vaccination triggering trained immune responses may play a role of protection against the COVID-19 pandemic³. A solid background on this rationale came recently from the interim analysis of the ACTIVATE trial. ACTIVATE (A randomized Clinical trial for enhanced Trained Immune responses through Bacillus Calmette-Guérin Vaccination to prevent infections of the Elderly) was a prospective randomized open-label controlled trial conducted among patients hospitalized at the 4th Department of Internal Medicine of ATTIKON University General Hospital in Greece. The protocol was approved by the National Ethics Committee of Greece and the National Organization for Medicine of Greece (EudraCT number, 2017-000596-87; ClinicalTrials.gov NCT03296423). The trial is conducted and funded by the Hellenic Institute for the Study of Sepsis. In this trial hospitalized elderly patients were vaccinated on the day of hospital discharge with single doses of placebo or BCG. Every patient is under follow-up for 12 months. The last visit of the last patient is scheduled for August 2020. An interim analysis took place on April 29th 2020 by an independent committee of experts. The full interim analysis (provided in APPENDIX I) focused on the study primary endpoint that was

the comparative time to a new infection between the two groups of treatment.

Infections counting against this primary endpoint were respiratory or viral infections necessitating medical treatment, community-acquired pneumonias, hospital-acquired pneumonias, intraabdominal infections, urinary tract infections, soft tissue infections and bloodstream infections. Analysis revealed 53% decrease of the incidence of new infections in the BCG group compared to the placebo group. This decrease reached 80% for all respiratory tract infections. Multivariate analysis showed that most of benefit was for patients with coronary heart disease (CHD) and chronic obstructive pulmonary disease (COPD). This interim analysis clearly enhances the concept that BCG can be protective against COVID-19.

AIM OF THE STUDY

The aim of the study is to demonstrate in a double-blind, placebo-controlled approach if vaccination of participants susceptible to COVID-19 with BCG vaccine may modulate their disease susceptibility for COVID-19. This will be validated using both clinical and immunological criteria. A sub-study will run in order to assess the mechanism of benefit from BCG vaccination on vascular endothelial function and on mononuclear blood cells.

STUDY DESIGN

Patient population

This is a prospective, multicenter, randomized, controlled trial in that will take place in departments in Greece (APPENDIX II). The study will be submitted for approval by the National Ethics Committee of Greece and by the National Organization for Medicines of Greece. Patients will be enrolled after written informed consent provided by themselves or provided by legal representative in case of patients unable to consent.

Inclusion criteria

Enrolled patients should meet all following inclusion criteria:

1. Written informed consent
2. Male or female

3. Age more than or equal to 50 years based on the precise date of birth. Female participants are allowed on the premise that they are post-menopausal.
4. History of at least one of the following: a) coronary heart disease; b) chronic obstructive pulmonary disease; c) Charlson's comorbidity index (CCI) more than 3 (APPENDIX III)
5. Skin tuberculin test diameter less than 10mm
6. Negative serum testing for immunoglobulin G and M against SARS-CoV-2

Exclusion criteria

Patients meeting ANY of the following should NOT be enrolled.

- Deny to written informed consent
- Age less than 50 years
- Known infection by the Human Immunodeficiency Virus-1 (HIV-1)
- Severely immunocompromised patients. This exclusion category comprises:
 - History of congenital immunodeficiency
 - History of solid organ transplantation
 - History of bone marrow transplantation
 - Intake of chemotherapy the last two months
 - Intake of radiotherapy the last two months
 - Active hemalogical or solid tumor malignancy
 - History of any anti-cytokine therapies
 - History of oral or intravenous steroids defined as daily doses of 10mg prednisone or equivalent for longer than the last 3 months

Study interventions

Participants will be randomized at 1:1 ratio by a separate list per study site into two treatment groups. The list of randomization will be generated by a biostatistician and the randomization will be in a sealed envelope. The envelope will be delivered to the attending physicians after randomization. The two groups of treatment will be as follows:

- Placebo group: these participants will receive one intradermal injection of 0.1ml of sodium chloride 0.9%

- BCG group: these participants will receive one intradermal injection of 0.1ml of BCG (Bacillus Calmette Guérin Moscow strain 361- I, Serum Institute for India)

Patient screening and enrolment (APPENDIX IV)

In order for screening to proceed, the study will be advertised in the study site of the Hellenic Institute for the Study of Sepsis (www.sepsis.gr) and in the sites of other medical societies. The text to be used for the study advertisement is provided in APPENDIX V. People who will collaborate for the patient information will be GCP certified by the Sponsor.

Screening may start only after written informed consent is provided. Once written informed consent is provided, screening follows the following order:

- The patient is screened against the exclusion criteria. If the patient does not meet any exclusion criteria, screening proceeds to the next step.
- The patient is screened for inclusion criteria 1 to 4. If he does not meet all of them, it is a screening failure and screening stops. If he meets all of them, screening proceeds to the next step.
- The PPD Skin Test (inclusion criterion 5) is performed with an intradermal tuberculin injection into an forearm according to the manufacturer's instructions. The patient is asked to return in 48 hours to measure the skin hardness. If the diameter of the skin hardness is greater or equal to 10mm, it is considered as failure and screening process ends. If the diameter of the skin hardness is less than 10mm, screening process proceeds to the next step. This step can be omitted for patients who have undergone tuberculosis skin testing or a positive indirect detection test for *Mycobacterium tuberculosis* by determination of interferon- γ (IFN γ) after excitation of the last CD4- /CD8- cells for special peptides (IGRA) within the past five (5) years. In this case, any skin reaction with a fraction of less than 10 millimeters or a negative IGRA test allows the patient to enter the study.
- For patients who continue screening process, a diagnostic test using blood from the fingertip to detect IgG/IgM antibodies against the SARS-CoV-2 virus takes place (inclusion criterion 6). If the test is positive for any of IgM or IgG antibodies, screening stops. If the test for both IgG / IgM antibodies is negative, the patient may be included in the trial.

Sub-Study

Participants who will be included in the study in the Department of Clinical Therapeutics of the ALEXANDRA General Hospital of Athens, will participate in a sub-study at the Vascular Laboratory of the Therapeutic Clinic. The sub-study procedures are carried out within the framework of the planned visits of the patients and are analyzed in the paragraph "Patient visits and interventions".

Study visits (APPENDIX IV)

Visit 1 This visit is conducted immediately after the end of the screening procedure (month 0 of study) and involves the following:

- Recording of the following information: age and gender, pre-existing comorbidities, history of hospitalizations the last two years
- For the participants of the sub-study, the following procedures will be performed:
 - a) carotid and femoral artery ultrasound, b) heart ultrasound, and c) a blood sample of 10 ml (peripheral blood) will be collected for PBMC stimulation for cytokine production (see section "Sub-study procedures")
- Administration of placebo or BCG

Visit 2 This visit is conducted 45 ± 5 days from the date of visit 1. This visit may be done by phone call or through the internet. During this visit, the vaccinated subject is asked to provide answers to a specific questionnaire involving the incidence of respiratory tract infection (Appendix VI). All patients will also be asked for the incidence of cardiovascular events, such as any diagnosis of stroke, myocardial infarction or rupture of a abdominal aortic aneurysm.

Visit 3 This visit is conducted 90 ± 5 days from the date of visit 1. This is a visit conducted at the study site. During this visit, the following are done:

- IgG and IgM antibodies against SARS-CoV-2 are measured in the vaccinated subject in exactly the same method that was followed at the screening stage
- The vaccinated subject is asked to provide answers to a specific questionnaire involving the incidence of respiratory tract infection (Appendix VI). All patients will

be asked for the incidence of cardiovascular events, such as any diagnosis of stroke, myocardial infarction or rupture of a abdominal aortic aneurysm.

- For the participants of the sub-study, the following procedures will be performed:
 - a) carotid and femoral artery ultrasound, b) heart ultrasound, and c) a blood sample of 10 ml (peripheral blood) will be collected for PBMC stimulation for cytokine production (see section "Sub-study procedures")

Visit 4 This visit is conducted 135 ± 5 days from the date of visit 1. This visit may be done by phone call or through the internet. During this visit, the vaccinated subject is asked to provide answers to a specific questionnaire involving the incidence of respiratory tract infection (Appendix VI). All patients will be asked for the incidence of cardiovascular events, such as any diagnosis of stroke, myocardial infarction or rupture of a abdominal aortic aneurysm.

Visit 5 This visit is conducted 180 ± 5 days from the date of visit 1. This visit may be done by phone call or through the internet. During this visit, the vaccinated subject is asked to provide answers to a specific questionnaire involving the incidence of respiratory tract infection (Appendix VI). All patients will be asked for the occurrence of cardiovascular events, such as any diagnosis of stroke, myocardial infarction or rupture of a abdominal aortic aneurysm. For the participants of the sub-study, the following procedures will be performed: a) carotid and femoral artery ultrasound, b) heart ultrasound, and c) a blood sample of 10 ml (peripheral blood) will be collected for PBMC stimulation for cytokine production (see section "Sub-study procedures")

It is explicitly stated that the investigators will encourage vaccinated population to refer to them in case of the incidence of any infection-related symptom.

PROCEDURES OF THE SUB-STUDY

Vaccinated people should abstain from food, alcohol and caffeine, smoking, and vasodilators for 12 hours before performing angiographic imaging studies. The exams to be taken are as follows:

- Arterial stiffness in the aorta from the speed of the pulse wave: It will be evaluated using a special non-invasive device (Complior, Artech Medical, France) in a non-bloody way on the carotid arteries and femoral arteries.
- Central blood pressure and reflected aortic waves: It will be evaluated using a special automated device (SphygmoCor System, AtCor Medical Pty Ltd, Sydney, Australia) in a non-bloody way on the carotid and femoral arteries.
- Endothelial function with ultrasound measurement of the dependent-from-the-endothelial dilation and mediated-from-the-nitrite dimension: It will be assessed using an ultrasound device and the measurement of the route-dependent vasodilator using a special 7-14 MHz audio recorder (Vivid 7 Pro, GE, USA) to be applied in a non-bloody way to the carotid and femoral arteries
- Carotid arteries intima-media thickness and Uterine Arteries: It will be evaluated using a B-mode ultrasound device and a special sound system (14.0 MHz multi-frequency linear array probe, Vivid 7 Pro, GE Healthcare, USA) in a non-bloody way on the carotid arteries. and femoral arteries.
- Cardiac ultrasound: The standard procedures of the clinical practice will be followed and the standard measurements will be taken using 2-D and Doppler ultrasound techniques.
- One blood sample will be taken from a forearm vein after antiseptic application and will be collected in tubes with anticoagulant agent. Isolation of PBMCs will be performed and they will be stimulated with purified bacterial antigens for cytokine production.

STUDY ENDPOINTS

Primary endpoint

The primary study endpoint is set on visit 3 (90 ± 5 days from the date of visit 1). The two groups of vaccination are compared for the primary endpoints which is composite. Patients who meet any of the following will be considered to meet the primary endpoint:

- Positive for the respiratory questionnaire endpoint when at least one of the following combination is met either at visit 2 and/or at visit 3 (see APPENDIX VI):
 - One situation definitively related to COVID-19

- All four questions of symptoms possibly related to COVID-19 answered YES
- At least two questions of symptoms possibly related to COVID-19 answered YES + need for admission at the emergency department of any hospital and/or need for intake of antibiotics answered YES
- At least four questions of symptoms probably related to COVID-19 answered YES one of which is “need for admission at the emergency department of any hospital and/or need for intake of antibiotics”
- Positive IgG or IgM antibodies against SARS-CoV-2

Secondary endpoints

The secondary endpoints are the difference between the two groups of vaccination in each of the following:

- Positive respiratory questionnaire endpoint (as defined above) on visit 4
- Positive respiratory questionnaire endpoint (as defined above) on visit 5
- Prevalence of IgG/IgM against SARS-CoV-2 among the total of screened participants
- Itemized analysis of each of the components of the respiratory questionnaire on each study visit
- The incidence of new cardiovascular events on each study visit
- Differences in repeated measurements of vascular parameters (arterial hardness, central arterial pressures, reflected waves, endothelial function and carotid medial sheath thickness) in visit 3 between the two sub-study groups (placebo or BCG)
- Differences in repeated measurements of vascular parameters (arterial hardness, central arterial pressures, reflected waves, endothelial function and thickness of medial carotid sheath) and cardiac ultrasound at visit 5 between the two sub-study groups (placebo or BCG)
- Changes in the release of cytokines from blood mononuclear cells at visit 3 between the two sub-study groups (placebo or BCG)

STUDY POWER CALCULATION

The study is powered for the primary endpoint. The results of the interim analysis of the ACTIVATE study reveal 20.4% incidence of total respiratory infections

after three months from vaccination in the placebo group and 12.2% in the BCG group. To demonstrate this difference with 90% power at the 5% level of significance, 437 people need to be vaccinated per group. To adjust for losses to follow-up, we target to enroll 450 people per group.

To estimate the power of the sub-study, it is anticipated that there will be a difference greater or equal to 2% in endothelial-dependent vasodilation between the two interventions in visit 5. A total sample of 68 patients (with equally 34 individuals in each study group placebo or BCG) will highlight a difference with a power of 80% at the 10% level of significance. In order to adjust for possible losses of 10%, it is estimated that 75 patients should be admitted to the sub-study.

STATISTICAL ANALYSIS

Comparisons between the two groups will be done by the Fisher exact test. Any value of p below 0.05 will be considered as significant.

The differences in the repeated measurements of the vascular parameters (arterial hardness, central arterial pressures, reflected waves, endothelial function and thickness of the inner-middle carotid sheath) will be estimated using randomly mixed models with two types: random effects (random intercept and random slope) and variance-covariance matrix. Vascular parameters will be used as dependent variables, after checking the normal distribution of their residuals with histograms and Q-Q plots graphs. In case of irregular distribution, appropriate transformations will be used (based on the neural index or using inverse ranking normalization).

INTERIM ANALYSIS

The Sponsor will appoint an independent committee to analyze the study and report the results of the primary endpoint once the last enrolled subject will reach visit 3. The study investigators will be informed on the results of the interim analysis but they will remain blind to the allocated arm of vaccination which will allow the study to end after the last visit of the last subject.

ADVERSE EVENTS

Adverse events (AEs) and Serious Adverse Events (SAEs) will be collected from baseline until the last patient's evaluation. Investigators should monitor subjects for adverse events and are responsible for recording ALL adverse events and serious adverse events occurring to a patient during the trial. Infection will not be reported as an SAE since this is the study primary endpoint.

An adverse event is any undesirable medical occurrence in a subject administered a pharmaceutical product and which does not necessarily have a causal relationship with this treatment. The time relationship is defined from the moment the AE occurs during therapeutic treatment until 30 days or 5 half-lives after treatment discontinuation. The adverse event may be a sign, a symptom, or an abnormal laboratory finding.

Serious adverse events (SAEs) must be reported to within 24 hours. If an adverse event meets any of the following criteria, it is considered SAE:

- **Death**
- **Life-threatening situation** The subject was at risk of death at the time of the adverse event/experience. It does not refer to the hypothetical risk of death if the AE were more severe or were to progress.
- **Inpatient hospitalization** or prolongation of existing hospitalization.
- **Persistent or significant disability/incapacity** Any AE having an outcome that is associated with a substantial disruption of the ability to carry out normal life functions, including the ability to work. This is not intended to include transient interruption of daily activities.
- **Congenital anomaly/birth defects** Any structural abnormality in subject's offspring that occurs after intrauterine exposure to treatment.
- **Important medical events/experiences** that may not result in death, be life-threatening, or require hospitalization may be considered a serious adverse event/experience when, based upon appropriate medical judgment, **they may jeopardize the subject and may require medical or surgical intervention to prevent one of the outcomes listed above**, i.e., death, a life-threatening adverse event/experience, inpatient hospitalization or prolongation of existing hospitalization, a persistent or significant disability/incapacity, or a congenital anomaly/birth defect. Examples of such medical events/experiences include

allergic bronchospasm requiring intensive treatment in an emergency room or at home, blood dyscrasias or convulsions that do not result in inpatient hospitalization, or the development of drug dependency or drug abuse.

- **Spontaneous and elective abortions** experienced by study subject.

A non-serious adverse event is any untoward medical occurrence in a patient or subject who is administered a pharmaceutical product, and which does not necessarily have a causal relationship with this treatment. A non-serious adverse event is one that does not meet the definition of a serious adverse event given.

Grading of severity

The severity of the adverse events shall be graded as:

- **Mild** the adverse event is transient and well tolerated by the patient
- **Moderate** the adverse events causes discomfort and affects the usual activities of the patient.
- **Severe** the adverse events affects the usual activities of the patient to an important degree and may cause disability or be life-threatening.

Relationship to the drug

The investigator will use the following definitions to assess the relationship of the adverse event to study drug:

- **Probably Related:** The adverse event has a strong time relationship to the drug or relapses if re-induced, and another etiology is improbable or clearly less probable.
- **Possibly Related:** The adverse event has a strong time relationship to the drug and an alternative aetiology is as probable or less probable.
- **Probably not Related:** The adverse event has a slight or no time relationship to the drug and/or there is a more probable alternative aetiology.
- **Unrelated:** The adverse event is due to an underlying or concomitant disease or to another pharmaceutical product and is not related to the drug (no time relationship and a much more probable alternative aetiology).

If an investigator's opinion of possibly related, probably not related or not related to study drug is given, an alternate etiology must be provided by the investigator. Please note that a severe adverse event/experience is not necessarily serious, as the term severe is a measure of intensity while a serious adverse event is determined based on the aforementioned regulatory criteria. Individual un-blinding

thought to be necessary for the management of an adverse event will be documented in the subject Case Report Form.

REFERENCES

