Abbreviation: ABSSSI: acute bacterial skin and skin structure infection

Table 3. Primary and Secondary Study Outcomes.

	Placebo (N=78)	BCG (N=72)	Odds Ratio (95% CI)	p-value
Patients with at least one new infection until month 12 — no. (%)*	33 (42.3)	18 (25.0)	0.46 (0.23-0.91)	0.04
Respiratory or viral infection necessitating medical treatment— no. (%)	14 (17.9)	3 (4.2)	0.20 (0.06-0.72)	0.01
Community-acquired pneumonia — no. (%)	8 (10.3)	3 (4.2)	0.38 (0.10-1.49)	0.21
Hospital-acquired pneumonia — no. (%)	2 (2.6)	0 (0)	-	0.50
Total respiratory infections — no. (%)	24 (30.1)	6 (8.3)	0.20 (0.08-0.54)	0.00
Intrabdominal infection — no. (%)	3 (3.8)	4 (5.6)	1.47 (0.32-6.81)	0.71
Urinary tract infection — no. (%)	6 (7.7)	8 (11.1)	1.5 (0.49-4.56)	0.58
Acute bacterial skin and skin structure infection — no. (%)	6 (7.7)	3 (4.2)	0.52 (0.13-2.17)	0.50
Bloodstream infection — no. (%)	2 (2.6)	0 (0)	-	0.49
Mean rate of hospitalization/patient until month 12 (SD)	0.49 (0.72)	0.43 (0.72)	N/A	0.63
Mean number of infections until month 12 (SD)	0.44 (0.61)	0.25 (0.52)	N/A	0.03
Mean courses of antibiotics until month 12 (SD)	0.69 (1.66)	0.60 (1.25)	N/A	0.44

One-year mortality — no. (%)	14 (17.9)	10 (13.9)	0.74 (0.31-1.78)	0.51
------------------------------	-----------	-----------	------------------	-------------

*some patients had more than one infection

Abbreviations: CI confidence interval; N/A not applicable; SD; standard deviation. * - differences in proportion with 95% CI, shown as percentages.

Table 4. Univariate and multivariate analysis of the effects of covariates on the incidence of at least one infection until month 12

Covariates	Univariate analysis			Multivariate analysis		
	OR	95% CI	p-value	OR	95% CI	p-value
Group of vaccination	0.46	0.23-0.91	0.03	0.43	0.21-0.88	0.02
Myocardial infarct	2.71	1.08-6.79	0.03	-	-	0.06
COPD	3.0	1.21-7.46	0.02	3.14	1.24-7.95	0.02

* Covariates that failed to enter the stepwise logistic regression model

Table 5. Sensitivity analysis of the incidence of new infections

	Placebo n/ total (%)	BCG n/total (%)	Difference			
			in proportion		OR	95% CI
			% (95% CI)			
Interim (150)	33/78 (42.3)	18/72 (25.0)	17.3 (2.1-31.3)	0.46	0.23-0.91	0.04
Total (198)	41/98 (41.8)	27/100 (27.0)	14.8 (1.6-27.4)	0.51	0.28-0.93	0.04

Abbreviations: CI: confidence interval; OR: odds ratio

Table 6. Adverse Events (AEs)

Serious AEs	Placebo (N=78)	BCG (N=72)	p-value
Presence of at least one SAE* — no. (%)	30 (38.5)	17 (23.6)	0.05

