APPENDIX VI Questionnaire addressed to patients on study visits

The questionnaire is composed of questions referring to symptoms possible related to COVID-19, probably related to COVID-19 and definitively related to COVID-19.

Did you present any of the following symptoms during the last 45 days (please answer with YES or NO to any of the following infections):	YES	NO
Symptoms possibly related to COVID-19		
• Cough for more than 48 hours without any other symptoms		
• Shortness of breath for more than 48 hours without any other symptoms		
• Fever above >38°C for more than 48 hours without any other symptoms		
• Expectoration for more than 48 hours without any other symptoms		
Symptoms probably related to COVID-19		
• Cough and shortness of breath for more than 48 hours		
• Cough and fever for more than 48 hours		
• Fever and shortness of breath for more than 48 hours		
• Fever and expectoration for more than 48 hours		
• Need for admission at the emergency department of any hospital		
• Need for intake of antibiotics		
Situation definitively related to COVID-19		
• Had known diagnosis of COVID-19 by molecular test		

Patients score positive for the respiratory questionnaire endpoint if they have one of the following combination:

- One situation definitively related to COVID-19
- All four questions of symptoms possibly related to COVID-19 answered YES

- At least two questions of symptoms possibly related to COVID-19 answered YES + need for admission at the emergency department of any hospital and/or need for intake of antibiotics answered YES
- At least four questions of symptoms probably related to COVID-19 answered YES one of which is “need for admission at the emergency department of any hospital and/or need for intake of antibiotics”

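### The primary endpoint can be met only through the participant's own answers at visits 2 and 3 or the on-site visit 3 antibody test, so a fatal COVID-19 case with no earlier positive cannot count as an event

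*Protocol*

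**What the plan says.** - **Timing and components (Study endpoints, Primary endpoint).** "The primary study endpoint is set on visit 3 (90 ± 5 days from the date of visit 1". A participant meets it through the respiratory questionnaire, when "at least one of the following combination is met either at visit 2 and/or at visit 3 (see APPENDIX VI", or through positive IgG or IgM. Nothing else is listed.
- **Source of the answers (Study visits).** At visits 2 and 3 "the vaccinated subject is asked to provide answers to a specific questionnaire". Appendix VI opens with "Did you present any of the following symptoms during the last 45 days". A molecular diagnosis is enough alone to score positive, but it too is a question put to the participant.
- **Antibodies (Study visits; Appendix IV).** At visit 3, "IgG and IgM antibodies against SARS-CoV-2 are measured in the vaccinated subject". After screening, no other antibody test is scheduled.
- **Mode of visit.** For visit 2, "This visit may be done by phone call or through the internet". Visit 3 is held at the study site, with no remote option.
- **Contact between visits.** The "investigators will encourage vaccinated population to refer to them in case of the incidence of any infection-related symptom", but no rule lets such a report score the endpoint.
- **Safety reporting (Adverse events).** Infection is kept out of SAE reporting on the ground that it is the primary endpoint.
- **Source of the planning rates (Appendix I).** ACTIVATE saw patients monthly and followed up new hospitalisations through discharge notes and, if needed, the treating physicians.

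**The concern.** The trial asks whether BCG protects against COVID-19, in people aged 50 or over with coronary disease, COPD or a Charlson index above 3. Deaths from the disease are plausible in that population. Yet a participant who is negative at visit 2 and dies on day 60 with a positive molecular test meets no listed criterion.

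Whether an event can be scored therefore depends partly on how severe it was. If BCG mainly lessened severity, survivors in the BCG arm could be scored while comparable fatal cases on placebo could not, and the comparison would lean against BCG. The SAE route is not sure to fill the gap, because infection is excluded there precisely on the assumption that the endpoint captures it. The planning rates come from a trial that used hospital and physician sources which this protocol does not name.

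**Working it through.** **1. Who can and cannot be scored under the written rule**

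| Course up to visit 3 | Can it be scored? |
|---|---|
| Positive at visit 2, then dies or misses visit 3 | Yes; a positive at either visit is enough |
| Ill, recovered, answers at visit 2 or attends visit 3 | In general yes: 45-day recall, reported molecular diagnosis or visit 3 antibodies |
| In hospital or isolation at visit 2, able to answer | Yes; visit 2 may be remote |
| No earlier positive, dies of COVID-19 before visit 3 | No |
| Too ill to answer at visit 2, no positive at visit 3 | No |
| No earlier positive, in hospital or isolation throughout days 85 to 95 | No; visit 3 is on site only |

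**2. The plan's own figure**

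Inputs (Study power calculation; Statistical analysis): 20.4% on placebo, 12.2% on BCG, 90% power, 5% significance (taken as two-sided), 1:1 allocation, Fisher exact test, 437 per group. The two-sided normal formula gives 425 per group with pooled variance and 449 with continuity correction, so 437 is reproduced within 3%. Exact Fisher power by enumeration is 89.6% at 437 and 90.4% at 450. The sample size is sound.

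**3. Effect on power if fatal cases are not scored**

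The documents give no rate of fatal COVID-19, so the rates here are assumptions. Let d be the proportion of an arm with a fatal event and no earlier positive.

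- Scored as non-events: observed rate = p − d.
- Dropped: observed rate = (p − d)/(1 − d), with 437 × (1 − d) analysed.

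| Assumed d, placebo / BCG | Observed if non-events | Difference | Exact power | Exact power if dropped |
|---|---|---|---|---|
| 0 / 0 | 20.4% / 12.2% | 8.2 points | 89.6% | 89.6% |
| 1% / 0.5% | 19.4% / 11.7% | 7.7 points | 86.8% | 88.7% |
| 2% / 1% | 18.4% / 11.2% | 7.2 points | 83.3% | about 85% |

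**4. A near-equal case taken from the documents**

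Appendix I, Table 3, row "One-year mortality", gives 14 of 78 and 10 of 72 deaths. Table 6 gives 8 and 5 after leaving out deaths from endpoint infections. The difference implies about 6/78 and 5/72 infection deaths in a year. At constant hazard over 90 days:

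- placebo: 1 − (1 − 6/78)^(90/365) = 2.0%
- BCG: 1 − (1 − 5/72)^(90/365) = 1.8%

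Subtracting gives 20.4 − 2.0 = 18.4% against 12.2 − 1.8 = 10.4%, a difference of 8.0 points. Exact power at 437 is 91.1%, slightly above baseline because lower rates carry less variance. These deaths cover all infection sites, the counts are small, and the patients had just left hospital at a mean age near 80.

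**5. Direction of bias**

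Suppose infection is truly 20.4% in both arms and BCG halves deaths from 2% to 1% (assumed). Scored as non-events, the observed rates are 18.4% on placebo and 19.4% on BCG, a 1-point shift against BCG. At 437 per arm the Fisher test rejects in 5.5% of such trials, with 4.8% of trials favouring placebo.

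**The case against.** The best case for the plan is that the gap is narrow. A reader might infer that anyone in hospital or isolation with COVID-19 during the window is lost. The documents do not support that: remote contact at visit 2, the 45-day recall, the reported molecular diagnosis and visit 3 antibodies catch most survivors, and a positive visit 2 stands whatever follows. This part of the objection holds, and only the three courses marked as not scorable remain.

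A reader might also infer that the lost participants are dropped or counted as non-events. The protocol does not say how a participant without visit 2 or 3 data is classified, and the SAP, which is not at hand, may. That also stands; both treatments are shown above only as illustrations. A missing-data rule would not, however, make death or a record-confirmed diagnosis a component of an endpoint whose components the protocol has fixed.

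It would go too far to say that most of any benefit disappears. The assumed scenarios keep 7.7 or 7.2 of 8.2 points. Nor is ACTIVATE's all-cause mortality a fair guide to size: its patients were older and newly discharged, whereas this trial enrols from age 50 and recruits through website advertisement. If BCG lessens severity, the bias runs against BCG and would not create a false claim of benefit.

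Finally, an infection endpoint without a mortality component can be a deliberate choice, since the stated aim concerns susceptibility. That does not explain why an infection proven by molecular test should fail to count because the participant died before being asked.

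**Conclusion.** The point holds in this limited form. Fatal COVID-19 with no earlier positive, and cases unable to answer or to attend throughout days 85 to 95 with no other positive, cannot meet the primary endpoint, even with a documented diagnosis. This follows from the endpoint definition in the protocol itself.

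The number affected is unknown. The power loss is modest, about 3 to 6 percentage points, and appears only under assumed fatal rates that are twice as high on placebo; with near-equal rates there is none to speak of. Those figures also assume that the planning rates include the fatal cases and that none of them had scored earlier. The more important matter is that loss depends on the outcome, which a larger sample cannot repair if severity differs by arm. This is a should-fix: cheap to settle, and best settled before unblinding.

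**What to change.** - **Endpoint definition.** State that a molecularly confirmed COVID-19 diagnosis, or death from COVID-19, between vaccination and the end of the visit 3 window counts as a primary endpoint event whatever the source: participant, relative, unscheduled contact, hospital record or death record. Require the same blinded ascertainment in both arms.
- **Visit 3.** Allow the questionnaire by phone or internet for those who cannot attend.
- **Sensitivity analysis.** Count every death before visit 3 as an event, in the protocol or the SAP.

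Hospital admission for any respiratory infection should not be added: it would widen the composite beyond the defect. The cost is a change of endpoint wording, a case report form page, one further analysis and some record retrieval by sites.
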